9.1.1. Other Aspects of Study Design

All clinicians who participate in this research will be required to complete Pfizer training related to the identification and reporting of AEs/serious adverse events (SAEs) and data abstraction training. AE/SAE training materials will be provided to the participating clinicians prior to any data collection. Once the provider has completed (electronically signed) the AE/SAE training, the providers will participate in a web-based data abstraction training. During this virtual training, CHSS research operations team members will review the AE/SAE training and answer any questions from providers. During this session, the providers will be asked to review their EMR systems to identify all patients treated with a GLAS-based regimen per the study selection criteria and generate a unique numeric identifier

for each patient. The total number of patients will be noted, including patients who received a GLAS-based regimen as second-line or greater, and the identifier maintained by CHSS research operations and the provider. CHSS will then ask the provider to randomly select one of the GLAS-treated patients. To randomly select patients, providers will sequentially number patients and provide those sequential numbers to CHSS Research Operations who will then use a random number generator to select one of the numeric patient identifiers. Providers will launch the data collection platform (web-based) and begin data abstraction for the patient. CHSS research operations will clarify any data points during this data collection process and observe the provider entering data into eCRF. After completing data abstraction, the providers will be sent electronic links to complete data abstraction for all remaining GLAS-treated patients over the course of the next 4 weeks. Providers will be given randomly selected patient numbers from the list of all GLAS-treated patients (excluding the 1 patient already submitted) and asked to complete data abstraction in the order of the randomly selected patients for the remaining patients.

9.2. Setting

Providers from OPEN will identify patients meeting the study selection criteria. OPEN is a community of over 7,000 oncologists, hematologists and urologists providing care to cancer patients geographically distributed across the US and practicing in both community and academic research settings. OPEN community members include medical doctors, nurse practitioners, pharmacists and other individuals providing care to cancer patients. Community members are not limited to any specific group purchasing organization or any other membership requirements. Community members are included in OPEN if they and their practice utilize Cardinal Health's proprietary Point-of-Care claims remittance software for practice management purposes or if they have participated in Cardinal Health sponsored research activities. Providers within the OPEN database are evenly distributed between regions (Northeast, Midwest, South, and West regions) across different size practices (small, medium, or large practice) and years of experience in providing cancer care.

To be eligible for participation in this research study, a board certified hematologist/oncologist must have treated or be treating at least 1 AML patient who meets the eligibility criteria for the study, agree to participate in a study sponsored by Pfizer, agree to complete and adhere to the Pfizer AE/SAE reporting protocols, and agree to conduct the initial data abstraction with CHSS research operations team members monitoring data entry into the eCRF. Providers must also be able to participate in the research monitored by a central Institutional Review Board (IRB). No site-specific IRB approval will be sought and providers requiring this approval will not be eligible.

After IRB approval of the research protocol, the eCRF will be pre-tested with 4 providers. Data collected as part of the pre-test will not be used in the final analytical dataset. After testing and revisions (if necessary), providers who completed a feasibility assessment for the research will be contacted and asked to participate in the research. Data collection will be conducted over the course of 4 weeks for each phase. Providers are compensated at fair

PFIZER CONFIDENTIAL

market value for each completed and verified eCRF assuming a rate of payment based on one hour of data collection and for the time required to complete the AE/SAE reporting and data abstraction training.

9.2.1. Inclusion criteria

Patients must meet all the following inclusion criteria to be eligible for inclusion in the study. Providers will be asked to confirm the criteria are met by answering a set of questions in the patient eligibility portion of the eCRF which correspond to these criteria. Automatic date and logic checks are employed to ensure that a patient identified is eligible for the study. For this study, the following inclusion criteria will be used:

- 1. Patients newly diagnosed with AML.
- 2. Initiated first-line or later therapy (i.e., index therapy) for newly diagnosed AML with GLAS-based regimen or initiated first-line therapy with VEN-based regimen in the following time periods*:
 - a. Initiated first-line or later therapy for AML with GLAS-based regimen between 01 December 2018 and 31 December 2019.^{\dagger}
 - b. Initiated first-line therapy for AML with VEN-based regimen between 01 December 2018 and 31 December 2019.
 - * These patients could have received systemic therapy for myelodysplastic syndrome (MDS, a precursor disease to AML, prior to diagnosis of AML).
 - [†] Patients who received GLAS as second-line or greater may be selected in Phase 4a pending the results of Phase 3.
- 3. ≥ 18 years of age at index therapy initiation.
- 4. \geq 6 months of follow-up from initiation of index therapy unless died, with known date of death.
- 5. Known cytogenetic risk profile at the time of index therapy initiation as defined below in Section 8.4.
- 6. ≥ 1 bone marrow biopsy completed following index therapy initiation.

9.2.2. Exclusion criteria

Patients meeting any of the following criteria will not be included in the study:

- 1. Patients who received treatment for AML as part of a clinical trial.
- 2. Patients with diagnosis of any other malignancy (except for non-melanoma skin cancer) at the time of treatment of AML.
 - a. Patients with diagnosis of AML and non-melanoma skin cancer at the time of treatment of AML will not be excluded.

PFIZER CONFIDENTIAL

3. A patient with a record of 1 or more of the following confounding diagnoses at any time during data availability: acute lymphoblastic leukemia; acute promyelocytic leukemia, aggressive systemic mastocytosis; hypereosinophilic syndrome and/or chronic eosinophilic leukemia; dermatofibrosarcoma protuberans; or gastrointestinal stromal tumors.

9.3. Variables

Providers: Provider characteristics include practice location, practice size, practice setting (e.g., community versus academic), urban versus rural location, years in practice, medical specialty, number of AML patients they personally see in an average month, and number of AML patients seen at their practice in an average month will be collected for each participating provider.

The following table summarizes the key variables to be collected from patient medical records via eCRF by treating physicians. Detailed definitions will be included in the statistical analysis plan (SAP) and case report form (CRF) documents which may include variables not listed below.

Table 9.3.1 Study Variables

Variable	Role	Operational definition	
Index therapy	Exposure	First-line therapy with GLAS or VEN for AML	
Age at AML diagnosis	Baseline characteristic	Calculated from date of AML diagnosis and year of birth	
Age at initiation of index therapy	Baseline characteristic	Calculated from date of initiation of index therapy and year of birth	
Sex	Baseline characteristic	M, F	
Race	Baseline characteristic	White, Asian, Black or African-American, Native Hawaiian or Other Pacific Islander, American Indian or Alaska Native, Other, Unknown	
Ethnicity	Baseline characteristic	As collected (Hispanic, non-Hispanic)	
3-digit zip and state	Baseline characteristic	As collected (for zip codes representing <20,000 people, zip code=000); Mapped to the US region as appropriate (Northeast, South, Midwest, West)	
Easter Cooperative Oncology Group performance score	Baseline characteristic	0, 1, 2, 3, 4, unknown	
Molecular profile	Baseline characteristic	NPM1, FLT3-ITD, IDH 1/2, K, TP53	
Provider assessment of cytogenetic risk status	Baseline characteristic	Favorable, Intermediate, Poor	
Cytogenetic abnormalities detected	Baseline characteristic	t(8;21)(q22;q22.1); RUNX1-RUNX1T1; inv(16)(p13.1q22) or t(16;16)(p13.1;q22) t(9;11)(p21.3;q23.3 t(6;9)(p23;q34.1); t(v;11q23.3); t(9:22)(q34_1;q11_2); inv(3)(q21_3q26_2) or	
		t(3;3)(q21.3;q26.2); -5 or del(5q); -7; -17/abn(17p); Complex karyotype,Monosomal karyotype	
Antecedent history of MDS	Baseline characteristic	Y/N (Yes: secondary; No: De novo) Date of MDS diagnosis	
Prior HMA therapy for MDS	Baseline characteristic/potential confounder	For patients who have antecedent history of MDS: HMA therapy regimen used (AZA, DEC, other please specify [open text])	
Serum creatinine	Baseline characteristic	mg/dL	
Neutrophils	Baseline characteristic	White blood cells (WBC)/microL	
Platelets	Baseline characteristic	micro/L	
Bone marrow blasts	Baseline characteristic	<pre><20-30, >30, missing/unknown</pre>	
Comorbidities including Charlson components	Baseline characteristic	A list with components of Charlson comorbidity index will be presented	
Cardiac disease	Baseline characteristic/potential confounder	Cardiac disease associated with conduction abnormalities or structural/functional deficits	
Pulmonary disease	Baseline characteristic/potential confounder	Restrictive or obstructive disorders	

PFIZER CONFIDENTIAL CT24-WI-GL02-RF02 1.0 Non-Interventional Study Protocol Template For Secondary Data Collection Study 15-Aug-2018 Page 23 of 35

Variable	Role	Operational definition
Liver disease	Baseline	Elevated alanine transaminase (ALT),
	characteristic/potential	aspartate transaminase (AST), alkaline
	confounder	phosphatase (ALP), or gamma-
		glutamyltransferase (GGT)
Renal disease	Baseline	Renal dialysis, renal transplant
	characteristic/potential	
	confounder	
Red blood cell (RBC)/platelet	Outcome	Date of first transfusion during index therapy
transfusion dependency (TD)		(both RBC and/or platelets), date of last
		transfusion during index therapy (both RBC
		and/or platelets)
		and platelet TD
Growth factors use	Outcome	Granulocyte colony-stimulating factor
	outcome	receptor (GCSF)
		lenograstim, filgrastim, long acting pegylated
		filgrastim, lipegfilgrastim
TI	Outcome	Defined as no RBC or no platelet transfusion
		for at least 56 consecutive days after initiation
		of index therapy) – provider reported
Reason for index treatment	Outcome	Efficacy of regimen, safety of regimen,
selection		quality of evidence, consistency of evidence,
		affordability of regimen, insurance approval
		time, patient choice, other
Number of cycles of index therapy	Outcome	Number/frequency of cycles of GLAS-based,
		VEN-based
Duration of index therapy	Outcome	Calculated by start and end dates of GLAS-
Pationala for treatment		Scheduled duration of therapy completed
discontinuation	Outcome	progression toxicity patient choice
AFs experienced during index	Clinical outcome	A list of AFs will be created and shown to
therapy with VEN	Chinear outcome	providers: an option for "other please
thorupy with very		specify" will be provided along with free text
		data entry. This list will include but not
		limited to tumor lysis syndrome, low WBC
		condition (e.g., infections, hemorrhage,

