Limited real-world observational studies of treatment patterns, outcomes, and safety for patients treated with either therapy have been conducted. Given the potential for a dramatic change in how patients are treated, it is critical that the scientific and medical communities continue to work to document the evolution of AML treatment over the coming years. The present study is focused on real-world outcomes in adult patients with AML who in the frontline received non-intensive therapy defined as GLAS-based (including GLAS+LDAC, GLAS+AZA, or GLAS+DEC) or VEN-based therapy (including VEN+LDAC, VEN+AZA, or VEN+DEC) in combination with other agents. Although the present study is focused on the receipt of this therapy during first-line therapy, it is expected that most of the identified patients will also go on to receive subsequent treatment. The aim of this study is to describe treatment patterns and effectiveness outcomes in a sample of oncology patients treated for AML with non-intensive first-line treatments.

This non-interventional study is designated as a Post-Authorization Safety Study (PASS) and is conducted voluntarily by Pfizer.

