9. RESEARCH METHODS

9.1. Study design

This study will be conducted through a multi-site medical chart review of AML patients treated at oncology clinics in the US. Providers in the Cardinal Health Oncology Provider Extended Network (OPEN) will be recruited to participate in the patient identification and data abstraction. All study data are secondary data and will have been collected retrospectively from existing clinical data originally collected as part of routine care.

Patient eligibility will be confirmed by the treating physician. Providers will abstract the patient level data necessary to achieve the research objectives into an electronic case report form (eCRF). No protected health information, except for dates of diagnosis, treatment, and outcomes, will be collected. The patients electronic medical record (EMR) will not be shared directly with Cardinal Health or Pfizer.

Two different types of AML patient cohorts will be identified as follows:

• GLAS-based: initiated first-line or later therapy (eg, index therapy) with GLAS+AZA, GLAS+DEC, GLAS+LDAC between 01 December 2018 and 31

PFIZER CONFIDENTIAL

CT24-WI-GL02-RF02 1.0 Non-Interventional Study Protocol Template For Secondary Data Collection Study 15-Aug-2018 Page 17 of 35 December 2019 (allowable combinations include GLAS plus low-dose cytarabine, GLAS plus azacytidine, or GLAS plus decitabine)

• VEN-based: initiated first-line (index) therapy with VEN+AZA, VEN+DEC, VEN+LDAC between 01 December 2018 and 31 December 2019 (allowable combinations including VEN plus low-dose cytarabine, VEN plus azacytidine, or VEN plus decitabine)

The study will be conducted in 5 sequential phases. The total proposed sample size across the 2 treatment arms is 150 patients. Figure 1 illustrates the study period.

Phase 1: Study Concept Feasibility

Cardinal Health Specialty Solutions (CHSS) research operations team, the investigator, will conduct outreach to OPEN inquiring as to the number of physicians who have prescribed GLAS per the study selection criteria. Providers will also be queried regarding their acceptance of the rules and conditions associated with participation in the research study.

Phase 2: eCRF Testing

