A total of 4 community oncologists will review the eCRF and abstract data for the purposes ensuring the requested clinical datapoints are available, the intent of the data point is clear, and the eCRF functions appropriately. Providers who participate in this testing phase are able to participate in further data collection. To test the eCRF providers will select 1 AZA-treated patient and complete data abstraction while Cardinal Health Specialty Solutions (CHSS) research operations team members watch data entry (via screen sharing), respond to questions from the providers, and ask questions of the providers as necessary. No data from this phase will be used in the final analytical dataset. After completion of eCRF testing, revisions to the eCRF will be made as necessary prior to the launch of study data collection.

Phase 3: Study Conduct Feasibility

CHSS will invite 15 providers who have indicated previously treating a patient with GLAS to participate in Phase 3. In Phase 3, each provider will abstract data for 1 GLAS-treated patient, randomly-selected, per the study selection criteria for a total of 15 patients. Providers will abstract data into the eCRF during a web-based, screen-sharing session with a member of the CHSS research operations team. Demographic, clinical, and disease-related characteristics of these patients, treatment patterns, and clinical outcomes will be described. After evaluating these data, Pfizer may elect to discontinue the study and not collect further data for either GLAS- or VEN-treated patients.

Phase 4a: GLAS Data Collection Expansion

Based on the results of Phase 3, Pfizer may elect to continue data collection. In addition, Pfizer may elect to expand data collection to include patients who received a GLAS-based regimen as second-line or greater should sufficient sample sizes of those patients be discovered during Phase 3 when provider enumerate all patient for whom they have prescribed a GLAS-based regimen. CHSS will allow data abstraction for the maximum number of GLAS-treated patients up to the total *a priori* sample size of 150 patients.

PFIZER CONFIDENTIAL

CT24-WI-GL02-RF02 1.0 Non-Interventional Study Protocol Template For Secondary Data Collection Study 15-Aug-2018 Page 18 of 35

Depending upon the number of GLAS-treated patients and the length of follow-up for these patients, Pfizer may elect to discontinue the study and not collect data for the VEN-treated cohort.

Phase 4b: VEN Data Collection

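### Index therapy is first-line only in Table 9.3.1 but first-line or later for GLAS in the cohort and eligibility text, so the GLAS outcome estimates can mix lines of therapy if the Phase 4a option is used

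*Protocol*

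**What the plan says.** The protocol gives two definitions of index therapy.

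**First-line only.** Table 9.3.1 (Section 9.3) lists index therapy as the exposure and defines it as "First-line therapy with GLAS or VEN for AML". Section 7 gives the aim as describing treatment patterns and "effectiveness outcomes in a sample of oncology patients treated for AML with non-intensive first-line treatments". The opening of Section 8 likewise asks about patients given frontline GLAS- or VEN-based therapy.

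**First-line or later, for GLAS.** Inclusion criterion 2 in Section 9.2.1 reads "Initiated first-line or later therapy (i.e., index therapy) for newly diagnosed AML with GLAS-based regimen", and item 2a repeats it: "Initiated first-line or later therapy for AML with GLAS-based regimen between 01 December 2018 and 31 December 2019". The cohort definition in Section 9.1 agrees: "initiated first-line or later therapy (eg, index therapy) with GLAS+AZA". The abstract carries the same criterion. For VEN, item 2b is first-line only: "Initiated first-line therapy for AML with VEN-based regimen between 01 December 2018 and 31 December 2019".

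**Later-line GLAS entry is optional.** The footnote to the inclusion criteria says "Patients who received GLAS as second-line or greater may be selected in Phase 4a pending the results of Phase 3". Under Phase 4a in Section 9.1, "Pfizer may elect to expand data collection to include patients who received a GLAS-based regimen as second-line or greater", on condition that enough such patients are found in Phase 3.

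**Analysis.** Table 9.3.1 starts time to best response, EFS, RFS and OS at initiation of index therapy and counts transfusion independence after it. Section 9.7.3 reports response, duration of response, transfusion independence, EFS/RFS and OS by treatment group, and plans adjusted hazard ratios for index therapy if the sample size permits. It does not mention the line at which the index regimen was started.

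**The concern.** Index therapy is both the exposure and the anchor for the outcomes. Several eligibility conditions are also timed from it: age, six months of follow-up, cytogenetic risk profile and the subsequent marrow biopsy. Two definitions of that term mean two possible primary cohorts.

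Under the table and the narrative, the GLAS cohort contains first-line starters. Under the eligibility text it may also contain patients who started GLAS at second line or beyond. Prognosis and response may well differ between these groups, so a single GLAS median OS or response rate would depend on the mix of lines and would not by itself answer the frontline question in Section 8. The decision to expand also follows the evaluation of Phase 3, in which patient outcomes are described, so the make-up of the primary cohort can change after some outcome data have been seen.

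Only GLAS can be later-line. In any adjusted GLAS-VEN hazard ratio, line of therapy would be entangled with cohort.

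**Working it through.** **Step 1. Compare the definitions.**

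| Place | GLAS index therapy | VEN index therapy |
|---|---|---|
| Table 9.3.1 | first-line | first-line |
| Section 7 (aim) and Section 8 (introduction) | first-line / frontline | first-line / frontline |
| Section 9.1, cohort definition | first-line or later | first-line |
| Section 9.2.1, criteria 2, 2a, 2b, and abstract | first-line or later | first-line |
| Section 8, numbered objectives 1 to 6 | no line restriction | no line restriction |

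VEN is consistent wherever a line is stated. GLAS is not. Section 5 records no amendments, so both definitions are current text.

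**Step 2. See whether the analysis text resolves it.** Section 9.7.3 works by treatment group and does not restrict, stratify or report by line of index therapy. Objective 2 asks for results by line of therapy up to two lines, but that covers treatment patterns, not survival or response. Table 9.3.1 lists the number of lines after index therapy and prior hypomethylating therapy for MDS. It lists neither the line number of the index regimen nor earlier AML therapy. Followed as written, the plan can mix lines within the GLAS estimates.

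**Step 3. Illustrate the size.** The protocol states no figure for this point, so there is none to reproduce. Inputs:

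- First-line median OS m1 = 8.3 months. This is an assumption: the number appears in Section 7 in a damaged sentence about the GLAS registration trial and cannot be attributed to an arm from the text.
- Later-line median OS m2 = 3 to 6 months. Assumed; not in the document.
- Later-line share w = 10%, 25% or 50%. Assumed; not in the document.
- Exponential survival in both groups. Assumed.

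The pooled median is the t that solves (1 − w)·2^(−t/m1) + w·2^(−t/m2) = 0.5.

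At w = 0.25:

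- m2 = 3: t = 6.33, since 0.75 × 0.589 + 0.25 × 0.232 = 0.442 + 0.058 = 0.500.
- m2 = 6: t = 7.63, since 0.75 × 0.529 + 0.25 × 0.414 = 0.396 + 0.104 = 0.500.

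| Later-line share | m2 = 3 | m2 = 4 | m2 = 5 | m2 = 6 |
|---|---|---|---|---|
| 0% | 8.3 | 8.3 | 8.3 | 8.3 |
| 10% | 7.5 | 7.7 | 7.9 | 8.0 |
| 25% | 6.3 | 6.8 | 7.3 | 7.6 |
| 50% | 4.8 | 5.6 | 6.4 | 7.0 |

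A 25% share therefore moves the pooled median down by 0.7 to 2.0 months (8.3 − 7.6 and 8.3 − 6.3).

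**Step 4. Set it against the likely cohort size.** The feasibility assessment in Section 9.5 found 39 GLAS patients. A 25% share of 39 is about 10 patients, so a few additions could make up a material part of the cohort.

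**The case against.** The strongest reply is that this is one row of a summary table plus some narrative wording. Section 9.3 says detailed definitions will be in the SAP and CRF, which may add variables, and Section 9.7.1 sends detailed methods to the SAP. Stratifying by line is ordinary SAP content. Much of this stands: the absence of a stratified analysis would not by itself be a finding against the protocol. What remains is that the protocol states an exposure definition that its own eligibility criteria contradict. Section 9.7.1 also says that major changes to primary endpoint definitions or analyses belong in a protocol amendment.

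Several stronger readings are tempting, and the documents do not support them:

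- *That a later-line GLAS patient has no time zero.* Read alone, Table 9.3.1 suggests this. Sections 9.1 and 9.2.1 identify the GLAS-based regimen as index therapy, so the start date is recoverable as the GLAS start.
- *That pooling is certain.* Later-line entry is optional, depends on Phase 3 and on sufficient numbers, and may never happen. No sentence says that the lines will share one estimate.
- *That the sponsor picks how many later-line patients to add.* The stated choice is whether to expand. Phase 4a then takes all GLAS patients or a random selection.
- *That a mixed cohort would match no stated population.* The numbered primary objectives cover patients who initiated a GLAS-based regimen, without a line restriction. The mismatch is with the frontline wording of Sections 7 and 8 and with Table 9.3.1.
- *That the added patients are relapsed or refractory.* The protocol says only second-line or greater and gives no reason for the change of line.

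One may also object that the abstract rules out GLAS-VEN comparisons. Section 9.7.3 nevertheless plans hazard ratios for index therapy, so the confounding matters wherever those are produced.

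**Conclusion.** The contradiction is real and sits in current text. Its consequence is conditional: if the Phase 4a option is used, the GLAS estimates of OS, EFS/RFS, response and transfusion independence can mix lines of therapy, and line would be confounded with cohort in the adjusted hazard ratios. If the option is not used, only the wording needs reconciling.

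The size is unknown. The shift to a pooled median of about 6.3 to 7.6 months at a 25% later-line share rests on assumed medians, an assumed share and exponential survival. It shows that the definition can matter materially, not that this study's estimate is wrong by that amount. The study is descriptive and has no a priori hypothesis, and the repair is small, so this is a should-fix point. The inconsistency itself is certain; the magnitude is only illustrative.

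**What to change.** 1. Reconcile Table 9.3.1 and Sections 7, 8, 9.1 and 9.2.1 to one definition of index therapy. For GLAS: the first GLAS-based regimen started in the enrolment window, at whatever line is eligible. For VEN: first-line only, as item 2b already says. A single common definition such as first GLAS or VEN regimen in the window would not do, because it would drop the VEN restriction.
2. Add the line number of index therapy to Table 9.3.1 as a baseline variable.
3. State in Section 9.7.3 that, if later-line GLAS patients are added, every GLAS outcome is reported separately for first-line and later-line starters. First-line starters answer the frontline question and are the only GLAS patients used in any GLAS-VEN hazard ratio.

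**Cost.** Wording and one eCRF field; Section 9.1.1 already has providers count second-line-or-greater GLAS patients. The statistical price is a smaller first-line set. Table 9.5.1 reproduces as 95% half-widths, 1.96·√(p(1 − p)/n): at p = 50% and n = 30 this gives 17.9 points, as printed. By the same formula, if 39 GLAS patients included 25% later-line (assumed), the first-line set would be about 29, and the half-width at 50% would grow from 15.7 to 18.2 points.
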